## **5.0 ADVERSE DEVICE EFFECTS**

An Adverse Device Effect (ADE) is an adverse event related to the use of a medical device. This includes:

- Any adverse event resulting from insufficiencies or inadequacies in the Instructions for Use, the deployment, the implantation, the installation, the operation, or any malfunction of the medical device
- Any event that is a result of a use error or intentional misuse.

Adverse Device Effects will be recorded as Adverse Events (AEs) and/or Device Complications (DCs).

### **5.1 Recording and Reporting Adverse Events**

An Adverse Event (AE) is defined as any untoward medical occurrence in a subject of a clinical investigation associated with use of an investigational product and that does not necessarily have a causal relationship with this product. An AE can therefore be any unfavorable and unintended sign (including an abnormal laboratory finding), symptom, or disease temporally associated with the use of an investigational product, whether or not related to use of the product.

#### **5.1.1 Recording Adverse Events**

Adverse events with an onset date following enrollment of the subject until the subject completes the study (is discharged) will be collected. Each adverse event will be followed until the adverse event has resolved or stabilized. Subjects should be encouraged to report adverse events spontaneously or in response to general, non-directed questioning. For each AE volunteered by the subject, the Investigator should obtain all the information required to complete the Adverse Event page of the CRF:

- Standard medical terminology for the AE
- Date and time of onset
- Severity of the event
- Relationship between the adverse event and the investigational product or related procedure
- Description of any subject therapy administered and actions required
- Outcome of the AE
- Whether or not the effect was serious and/or unanticipated

All AEs, regardless of seriousness, severity, or presumed relationship to study intervention must be recorded using medical terminology in the source document and on the adverse experience case report form.

Whenever possible, a diagnosis should be given when signs and symptoms are due to common etiology (e.g., cough, runny nose, sneezing, sore throat, and head congestion should be reported as "upper respiratory infection").

Each adverse event should be reported separately. For example, “nausea and vomiting” should be split into two separate events.

All AEs must be followed until resolution or until a stable clinical endpoint is reached. All measures required for AE management and the ultimate outcome of the AE must be recorded in the source document and reported to the Sponsor.

#### 5.1.2 Laboratory Abnormalities

An abnormal laboratory result not explained by a recorded clinical diagnosis or condition will be considered an adverse event if it is:

- Grade 3 or 4,
- Clinically significant (requires further diagnostic testing or treatment), or
- Considered to be an Adverse Event by the Investigator.

#### 5.1.3 Grading Severity of Adverse Events

The severity of AEs will be graded as follows:

Mild	Awareness of a sign or symptom that does not interfere with the patient’s usual activity or is transient, resolved without treatment and with no sequelae.
Moderate	Interferes with the patient’s usual activity and/or requires symptomatic treatment.
Severe	Symptom(s) causing severe discomfort and significant impact of the patient’s usual activity and requires treatment.

#### 5.1.4 Assigning Relationship of Adverse Events to Study Product

A relationship must be assigned by the Investigator to each reported adverse event, and will be documented as follows:

Not related	The cause of the AE is known and the event is not related to any aspect of study participation.
Unlikely to be related	There is little or no temporal relationship to the study device and/or a more likely alternative etiology exists.
Possibly related	There is a reasonable possibility that the event may have been caused by study participation. The AE has a timely relationship to the study procedure(s); however, follows no known pattern of response , and an alternative cause seems more likely or there is significant uncertainty about the cause of the event.
Probably related	It is likely that the event was caused by study participation. The AE has a timely relationship to the study procedure(s) and follows a known pattern of response ; a potential alternative cause, however, may explain the event.

Related	A related event has a strong temporal relationship and an alternative cause is unlikely.
----------------	---

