## 5.3 Unanticipated Adverse Device Effects

Any SAE that has been determined to be device or procedure-related should be further classified as anticipated or unanticipated. An unanticipated adverse device effect (UADE) is any serious adverse effect on health or safety, any life-threatening problem or death caused by, or associated with a device, if that effect, problem, or death was not previously identified in nature, severity, or degree of incidence in the application; or any other unanticipated serious problem associated with a device that relates to the rights, safety, or welfare of subjects.

Investigators must report any (potential) unanticipated adverse device effects to the sponsor and their IRB as soon as possible but no later than within 10 working days after the investigator first learns of the event [21 CFR 812.150]. UADEs should be reported immediately via telephone or email to the Sponsor Safety Officer as well as on the eCRF.

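### One relatedness rating joins device and procedure and changes its referent between levels, so the serious adverse device effect count cannot be reliably derived from the protocol text

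*Combined protocol and SAP*

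**What the plan says.** Sections 3.2.2 (Safety Endpoints) and 6.4 list three safety endpoints: device- and procedure-related adverse events taken together, serious adverse events, and serious adverse device effects. Section 5.0 makes the third device-specific: "An Adverse Device Effect (ADE) is an adverse event related to the use of a medical device". The documents define adverse device effect but not its serious form.

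Section 5.1.1 lists what the adverse event page must capture, including "Relationship between the adverse event and the investigational product or related procedure". Section 5.1.4 is headed as relationship to the study product and states: "A relationship must be assigned by the Investigator to each reported adverse event, and will be documented as follows". Five levels follow:

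- *Not related*: "The cause of the AE is known and the event is not related to any aspect of study participation".
- *Unlikely*: "There is little or no temporal relationship to the study device and/or a more likely alternative etiology exists".
- *Possibly*: a reasonable possibility of causation by study participation, timely to the study procedure(s), no known response pattern, and either "an alternative cause seems more likely or there is significant uncertainty about the cause of the event".
- *Probably*: "It is likely that the event was caused by study participation", timely to the study procedure(s), with a known pattern, although another cause may explain the event.
- *Related*: strong timing and no likely alternative, with no referent named.

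Section 5.3 keeps the two causes joined: "Any SAE that has been determined to be device or procedure-related should be further classified as anticipated or unanticipated". Section 6.6.3 tabulates by relatedness to yet another term, study intervention.

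**The concern.** The device-effect endpoint needs to know whether the EBBMS caused the event. The protocol text asks only whether the device or a related procedure did, on a scale whose levels do not share a referent. Every subject has a large-bore femoral procedure with its own bleeding and vascular risks. Section 5.5.1 lists bleeding, hematoma and vascular trauma among the possible risks of using the device. Section 4.3.2 puts the EBBMS in the femoral vein first and then allows large-bore access on the same side, so both sources of harm can lie in one groin.

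No control arm is described from which background harm could be estimated, and section 1.2.2 reports no earlier human use. Event-level attribution is therefore the main route to a statement about device harm. If it depends on how each site reads the scale, so does the reported count.

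**Working it through.** The plan states no figure on this point, so there is none to reproduce. The check compares the texts and then gives a bounding illustration.

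**Step 1. Referent by level (section 5.1.4)**

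| Level | Cause judged against | Timing judged against |
|---|---|---|
| Not related | any aspect of study participation | not stated |
| Unlikely | an alternative etiology being more likely | study device |
| Possibly | study participation | study procedure(s) |
| Probably | study participation | study procedure(s) |
| Related | not named | not named |

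The section heading (study product), the CRF item in 5.1.1 (product or related procedure) and 6.6.3 (study intervention) add three more terms.

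**Step 2. One event under two readings.** Take a serious groin hematoma on the side carrying both sheaths.

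- *Reading A.* Participation means what the study adds: the EBBMS, its monitoring, the CT and the blood tests. The index procedure was already planned (3.3.1) and follows institutional practice (3.5, 3.6.3). The large-bore sheath is then a more likely cause than the study device, and the event rates *Unlikely*.
- *Reading B.* Participation includes the index procedure, which section 3.6 lists among the study procedures (as 3.6.3). The event is timely and follows a known pattern, so it rates *Probably*.

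Both readings follow the text. The first would ordinarily leave the event out of the device-effect count and the second would put it in. Because 5.1.4 sets no threshold, even that last step is left to the analyst.

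**Step 3. Overlap of *Unlikely* and *Possibly*.** *Unlikely* is met by a likelier alternative alone, because its two conditions are joined by and/or. *Possibly* can also be met when an alternative seems likelier, provided that the event is timely and has no known pattern. Such events fit both levels. The hematoma in step 2 has a known pattern, so this is a separate and narrower fault.

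**Step 4. Other records.** Section 5.4 covers device deficiency, malfunction, use error and misuse. A vessel injury from a sheath that worked as intended falls outside it. Section 5.3 splits related serious events only into anticipated and unanticipated.

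**Step 5. Illustration.** Inputs: n = 100 (section 6.1), and k subjects with one serious event each rated related, where k is assumed. With device and procedure joined, the device-effect count can be any whole number from 0 to k. Exact (Clopper-Pearson) 95% limits for x of n are

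lower = Beta quantile(0.025; x, n − x + 1), upper = Beta quantile(0.975; x + 1, n − x).

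For x = 0 the lower limit is 0 and the upper limit is 1 − 0.025^(1/100) = 0.036.

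| Assumed k | If none is a device effect | If all are device effects |
|---|---|---|
| 2 | 0% (0 to 3.6%) | 2% (0.2 to 7.0%) |
| 3 | 0% (0 to 3.6%) | 3% (0.6 to 8.5%) |
| 5 | 0% (0 to 3.6%) | 5% (1.6 to 11.3%) |
| 10 | 0% (0 to 3.6%) | 10% (4.9 to 17.6%) |

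**The case against.** Several points on the other side stand.

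- **The CRF is not in the documents.** It could hold separate device and procedure fields. The point is therefore about the protocol text, and it would be wrong to say that the data cannot separate the two.
- **Two of the three safety endpoints are untouched.** One pools device and procedure by design, and serious adverse events need no attribution.
- **Case review is feasible.** Serious events are listed and have written reports (5.2.2, 6.6.3), and with about 100 subjects they can be read one by one. But the protocol describes no adjudication of relatedness, and reconstructing a cause afterwards does not replace recording it.
- **The aims are modest.** Objectives are preliminary, the study is descriptive, and no safety hypothesis is tested.

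A reader might infer more than the text supports:

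- *That every large-bore hematoma would be rated Probably and counted against the device.* Under reading A it rates *Unlikely*. The fault is that both ratings are open.
- *That unanticipated device effects would be missed.* Section 5.3 admits device- or procedure-related serious events and asks for potential cases, and 5.2.2 sends all serious events to the sponsor within 24 hours. Separate ratings would not change what enters that route.
- *That the 5.4% in section 1.1 is the expected rate.* It is major bleeding with transfusion in a registry of coronary interventions, not access-site bleeding. The access-site figures there are 1.8% (hematoma needing transfusion) and 23.8% of 3.9%, or 0.238 × 3.9% = 0.9%. None of these registries is described as a large-bore cohort.

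**Conclusion.** The point holds for the serious adverse device effect endpoint. From the protocol text, its count cannot be derived reliably: one rating joins two causes, the referent changes between levels, the endpoint is undefined, and no level marks an event as related. The overlap of *Unlikely* and *Possibly* is a second, smaller fault, confined to timely events with no known pattern and a likelier alternative cause.

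The size depends on an assumed k. At k = 2 the estimate lies between 0% and 2%, with an outer upper limit of 7.0%. At k = 5 it lies between 0% and 5%, with an outer upper limit of 11.3%. These are the extremes that the text permits, not an expected error. The ambiguity exists for any k above zero. The primary kappa analysis is not affected. The change should be made before enrollment, because attribution not recorded at the time would have to be rebuilt later.

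**What to change.** 1. In 5.1.1 and 5.1.4, record two ratings per adverse event: one for the EBBMS device, including its insertion, use and removal, and one for the index endovascular procedure.
2. At every level of each scale, including *Related*, replace study participation and study procedure(s) with the named referent. Without this step the two ratings could still share one meaning.
3. In *Possibly*, shorten "an alternative cause seems more likely or there is significant uncertainty about the cause of the event" to its second half, so that only uncertainty about the cause remains and the overlap with *Unlikely* is removed.
4. Define a serious adverse device effect as a serious adverse event rated *Possibly* or higher on the device scale.
5. Align the terms in 5.3 and 6.6.3 with the two ratings, without narrowing what is reported.

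The cost is one extra CRF field, a few lines of text and brief site training. Some bleeds on the side carrying both sheaths will remain hard to attribute, and a threshold at *Possibly* may still count many of them. Showing both ratings for each serious event would make that visible.

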## 5.2 Serious Adverse Events

### 5.2.1 Definition of a Serious Adverse Event

A Serious Adverse Event (SAE) is defined as any event meeting any of the following criteria:

- Is life-threatening (immediate risk of death) or fatal
- Requires, or significantly prolongs, inpatient hospitalization
- Results in persistent or significant disability and/or incapacity
- Is a congenital anomaly or birth defect
- Requires medical or surgical intervention to prevent one of the outcomes listed above

### 5.2.2 Reporting SAEs

Serious Adverse Events (SAE) will be reported to the Sponsor's Safety Officer within 24 hours of the Investigator becoming aware of the event, and a written report provided within 3 business days to:

[name]., M.D.  
 [contact]  
 [contact]

A Serious Adverse Event report will be prepared and will contain as much available information concerning the event as possible so that a written report may be filed with the FDA.

In accordance with Federal regulations, Investigators will be notified of the occurrence of serious and unexpected adverse events. The Investigator must promptly inform the relevant Institution Review Board in accordance with the IRB's policies.

Documentation of submission of SAEs to the IRB must be forwarded to Proxima and the Sponsor and retained in the Investigator's Study File.

## 5.3 Unanticipated Adverse Device Effects

Any SAE that has been determined to be device or procedure-related should be further classified as anticipated or unanticipated. An unanticipated adverse device effect (UADE) is any serious adverse effect on health or safety, any life-threatening problem or death caused by, or associated with a device, if that effect, problem, or death was not previously identified in nature, severity, or degree of incidence in the application; or any other unanticipated serious problem associated with a device that relates to the rights, safety, or welfare of subjects.

Investigators must report any (potential) unanticipated adverse device effects to the sponsor and their IRB as soon as possible but no later than within 10 working days after the investigator first learns of the event [21 CFR 812.150]. UADEs should be reported immediately via telephone or email to the Sponsor Safety Officer as well as on the eCRF.

## 5.4 Device Complications

Investigators are instructed to report all possible device deficiencies, malfunctions, misuse or use error observed during the course of the trial. These incidents will be documented in the case report form provided as follows:

**Device deficiency:** Inadequacy of a medical device related to its identity, quality, durability, reliability, safety or performance. Device deficiencies include malfunction, use error, and inadequate labeling. They may or may not affect device performance or lead to an adverse event.

**Device malfunction:** Failure of an investigational medical device to perform in accordance with its intended purpose when used in accordance with the Instructions for Use (IFU) or protocol. device malfunction occurs when the device is used in compliance with the IFU but does not perform as described in the IFU.

**Use error:** Act or omission of an act that results in a different medical device response than intended by the manufacturer or expected by the user. Use error includes slips, lapses and mistakes. An unexpected physiological response of the patient does not itself constitute a use error.

**Device misuse:** Any use of the investigational device by an investigator that is contradictory to the application described in the Instructions for Use will be categorized as device misuse. This is a form of Use Error.

## 5.5 Risk/Benefit Analysis

### 5.5.1 Potential Risks and Discomforts

Enrollment in the trial involves exposure to some risks. Most risks of trial participation are not materially different than those encountered by an individual undergoing a large bore endovascular procedure outside the context of the trial as introducer sheaths are normally used to access the targeted vessels with the Early Bird. However, the use of the Early Bird device may involve exposure to additional risks as well as other potential risks of an unknown nature.

- Blood loss, bleeding or hematoma
- Embolization (micro or macro) with transient or permanent ischemia
- Infection or scarring
- Vascular trauma (dissection, rupture, perforation, tear etc.)
- There is a risk that the procedure may not detect an internal bleed.
- There is a risk of improper use of the device due to inadequate specifications or training.

### 5.5.2 Methods to Minimize Risks

- Before releasing the patient, confirmation of internal bleeding status with non-contrast CT scan.
- Adequate IFU to ensure proper technique.

- Only doctors who have been trained in the use of the Early Bird device will participate in the study
- Only doctors with the necessary experience in large bore endovascular procedures will participate in this study

#### 5.5.3 Potential Benefits

- Early detection of internal bleeds during the endovascular procedure
- Less or no need for blood transfusions
- Reduction in, or no drop in post-procedural hemoglobin levels.

## **6.0 STATISTICAL CONSIDERATIONS**

### **6.1 Patient Sample Size Requirements**

This study is intended to describe the accuracy and safety of the Saranas EBBMS. A sample of approximately 100 subjects should provide adequate evaluation of the planned endpoints. If 5%,  $n = 5$ , of subjects experience a bleed as detected by either the Saranas EBBMS or computerized tomography then the Kappa score remains above 0.7 when there are two or fewer discordant pairs. The 95% confidence interval with two discordant pairs and Kappa of 0.74 ranges from 0.39 to 1.0.

### **6.2 Primary Efficacy Endpoint**

The primary endpoint is the level of agreement in bleeding detection between the Saranas EBBMS and post-procedural computerized tomography.

### **6.3 Secondary Endpoints**

The following secondary endpoints will be assessed:

- Level of agreement in bleeding detection between the Saranas EBBMS and clinical assessment or post-procedural computerized tomography
- Device sensitivity in bleeding detection of the Saranas EBBMS as compared to post-procedural computerized tomography
- Device specificity in bleeding detection of the Saranas EBBMS as compared to post-procedural computerized tomography
- Device sensitivity in bleeding detection between Saranas EBBMS and clinical assessment or post-procedural computerized tomography
- Device specificity in bleeding detection between Saranas EBBMS and clinical assessment or post-procedural computerized tomography
- Relationship between level (severity) of bleed detected by the Saranas EBBMS and the severity of bleeding as assessed by computerized tomography
- Relationship between level (severity) of bleed detected by the Saranas EBBMS and the severity of bleeding as assessed by the absolute drop in hemoglobin
- Relationship between level (severity) of bleed detected by the Saranas EBBMS and the number of transfusions
- Relationship between level (severity) of bleed detected by the Saranas EBBMS and the severity of bleeding as assessed by VARC-2 criteria.
- Relationship between level (severity) of bleed detected by the Saranas EBBMS and the occurrence of post-procedural acute kidney injury

## **6.4 Safety Endpoints**

From enrollment until end of study, all:

- Device and procedure-related adverse events
- Serious adverse events
- Serious adverse device effects

## **6.5 Study Populations**

*Intent to Treat Population:* The Intent to Treat (ITT) population is defined as all subjects who were enrolled in the study.

*Per Protocol Population:* The Per Protocol (PP) population is defined as all subjects who had a post-procedure computerized tomography.

*Safety Population:* The Safety Population is defined as all subjects who are enrolled, who receive study intervention, and who have some post-baseline assessment of safety data.

## **6.6 Statistical Analytical Plan**

### **6.6.1 Demographics and Subject Characteristics**

For all subjects included in this study, baseline demographic and medical history data will be summarized for each treatment group. Summaries for quantitative variables include the sample size, mean, median, standard deviation, minimum, and maximum. Summaries for categorical variables include the number and percent of patients for each outcome. No statistical testing will be performed to compare these factors. These summaries will be conducted in the all three populations, ITT, PP and Safety.

### **6.6.2 Assessment of Endpoints**

#### Primary Endpoint

The primary endpoint is the level of agreement in bleeding detection between the Saranas EBBMS and post-procedural computerized tomography. Each case will be defined dichotomously as bleed or no bleed by both techniques. This analysis will be conducted in the PP population of subjects who has a post-procedure computerized tomography.

Level of agreement will be assessed using Cohen Kappa statistic. A 95% confidence interval will be applied. A good Kappa score is considered to be at 0.6 or greater. for dichotomous endpoints. Each case will be defined as a bleed or no bleeding.

